12. INDEPENDENT DATA MONITORING COMMITTEE (IDMC)

An external IDMC will periodically review cumulative unblinded data to evaluate safety during the study. The IDMC will be convened regularly, at least twice a year, and *ad hoc* as needed. It is the responsibility of the IDMC to weigh the risks and benefits of study treatment throughout the duration of the trial, to include monitoring evidence for treatment harm (eg, toxicity, AEs, SAEs, and deaths) and requesting additional data analyses as necessary for the safety review process. The IDMC can recommend stopping the study for safety reasons based on their review and findings. IDMC recommendations will be provided to Kezar.

Details regarding the composition, scope, conduct, processes, and responsibilities of the IDMC are detailed in a separate IDMC Charter.

13. CHANGES IN THE PLANNED ANALYSIS

- Analysis of opportunistic infections has been added in the SAP, Section 9.1.6.
- In the Protocol Section 10.6, jump to placebo and tipping point imputation analyses are mentioned as a method for dealing with missing data in general. However, in the SAP, we have removed these analyses for non-key secondary endpoints.
- Respiratory rate has been added to this SAP because it was inadvertently omitted from the Protocol, but was routinely collected during conduct of the study.
- Clarification that "Time to UPCR ≤0.5" is considered a secondary efficacy study endpoint, as this is mentioned as a 'variable' in Protocol Section 10.6: "For time-to-event variables (eg, time to CRR, time to PRR, and time to UPCR ≤0.5), the Kaplan Meier method...". This has been added to Table 1 in the SAP.
- The number of sites and countries has been updated in the SAP to "Approximately 214 sites from ~21 countries worldwide are planned to participate in this study" which differs from the number mentioned in the Protocol and is more accurate.
- Intercurrent events as defined in the Protocol (Table 6) were redefined and provided with clear labels in Section 8.2.1, for the purpose of the SAP. For example, non-responder events were combined under Treatment Failure (by definition) and Death was added.
- A Tertiary Estimand has been added to this SAP (for the PP Population) compared with the Protocol which called the analysis with the PP Population a 'supportive' analysis.
- Per Protocol, Section 10.6.1.1 states "For patients whose CRR at Week 37 cannot be adequately determined (including missing data, early study discontinuation, or lost to follow-up), their CRR will be imputed using an NRI approach.". In the SAP, Section 8.2.1, early study discontinuation, or lost to follow-up are being managed using the Estimand framework, see SAP, Table 5.
- The protocol Section 10.6.1, states: "Supplemental analyses on the primary and selected key secondary endpoints may be performed using logistic regression models. These analyses will include covariates for treatment, UPCR at baseline (stratification factor), biopsy class, IV methylprednisolone use at Baseline (stratification factor), and region and other selected baseline parameters." However, in the SAP, Section 8.2.3.1 we specify that the baseline 24-hour UPCR value (as a continuous number) will be used instead of the categorical strata factor by stating: "The model will include covariates for treatment, stratification factors (LN Class, IV methylprednisolone), baseline 24-hour UPCR value (as a continuous number, not a stratification factor), and geographic region."

- Added 3 new exploratory endpoints to the SAP which were not included in the Protocol:
 - Time to antibodies normalization or negative status (anti-dsDNA antibody normalization, anti-C1q antibody negative status)
 - Time to complement (C3, C4) no longer being low
 - Change from Baseline in IgM, IgG, and IgA
- It should be noted that there is no reference to the sponsor's Steering Committee (SSC) in the SAP because Kezar has decided not to form and include a SSC in this study.
- The following analytes have been added to Table in Appendix 12:
 - neutrophil count
 - Anti-dsDNA
 - Complement (C3 and C4)
 - C1q autoantibody
 - Quantitative immunoglobulins (immunoglobulins M, G, and A)
 - white blood cells
 - red blood cells
 - 24-hour UPCR
 - FMV UPCR
 - 24-hour Proteinuria (Urine Protein (24hr))

15. APPENDICES

APPENDIX 1. SCHEDULE OF ASSESSMENTS

Site Visit Week	Sc	1	2	5	9	13	17	21	25	29	33	37	41	45	49	53 EOT	56 EOS ^a	ETV
Assessment Window (days)	-35 to -1	NA	±2	±2	±2	±2	±2	±2	±2	±2	±2	±2	±2	±2	±2	±2	±2	NA
Informed consent	X																	
Medical history, including prior medications	X																	
Infectious disease blood tests ^b	X																	
Serum pregnancy test	X																	
Hepatitis B DNA ^c		X				X			X			X				X	X	X
Chest x-ray ^d	X																	
EULAR/ACR criteria for SLE	X																	
Physical examination ^e	X	X	X	X	X	X	X	X	X	X	X	X	X	X	X	X	X	X
12-lead ECG with QTcF interval ^f	X								X							X		X
Vital signs ^g	X	X	X	X	X	X	X	X	X	X	X	X	X	X	X	X	X	X
Clinical lupus disease assessmentsh	X	X				X			X			X				X	X	X
EQ-5D-5L		X				X			X			X				X	X	X
GTI assessment (including labs ⁱ)		X							X							X		X
Estimated GFR	X	X		X	X	X	X	X	X	X	X	X	X	X	X	X	X	X
Clinical laboratory tests ^j	X	X		X	X	X	X	X	X	X	X	X	X	X	X	X	X	X
Anti-dsDNA and complements (C3 and C4)	X	X		X	X	X	X	X	X	X	X	X	X	X	X	X	X	X
C1q autoantibody and quantitative IgM, IgG, IgA		X				X			X			X				X	X	X
Urine pregnancy test ^k		X		X	X	X	X	X	X	X	X	X	X	X	X	X	X	X
24-hour urine test	X					X			X			X				X	X	X
First morning void urine test	X			X	X	X	X	X	X	X	X	X	X	X	X	X	X	X
IV methylprednisolone ^l		X																
Background medications ¹	•																	\rightarrow

Site Visit Week	Sc	1	2	5	9	13	17	21	25	29	33	37	41	45	49	53 EOT	56 EOS ^a	ETV
Zetomipzomib or placebo administration ^m			← ze	tomipa	zomib	or plac	cebo a	dminis	tration	ı from	Week	1 to V	Veek 5	52 →				
Renal histopathology and immunohistopathology ⁿ	X															X		X
Urine biomarker measurements	X					X			X			X				X	X	X
Blood biomarker measurements ^o		X				X			X			X				X	X	X
Sparse PK assessment ^p									X			X						
Optional PK assessment ^p				X														
AEs and concomitant medications ^q	(AEs a	and con	ncomit	ant me	edicati	ons co	llected	l from	Week	1 to V	Veek 5	2, We	ek 53,	Week	56, and	etv →	

ACR=American College of Rheumatology; AEs=adverse events; anti-dsDNA=anti-double stranded DNA; CBC=complete blood count; DNA=deoxyribonucleic acid; ECG=electrocardiogram; eCRF=electronic case report form; EOS=End of Study; EOT=End of Treatment; EQ-5D-5L=EuroQol 5-Dimension 5-Level; ETV=Early Termination Visit; EULAR=European Alliance of Associations for Rheumatology; GFR=glomerular filtration rate; GTI=Glucocorticoid Toxicity Index; HbA1c=hemoglobin A1c; HbcAb=hepatitis B core antigen antibody; HBsAb=hepatitis B virus surface antibody; HBsAg=hepatitis B virus surface antigen; HIV=human immunodeficiency virus; Ig=immunoglobulin; IgA=immunoglobulin A; IgG=immunoglobulin G; IgM=immunoglobulin M; MMF=mycophenolate mofetil; MPA=mycophenolic acid; NA=not applicable; PGA=physician global assessment of disease activity; QTc=QT interval corrected; SLE=systemic lupus erythematosus (includes lupus nephritis); SLEDAI-2K=Systemic Lupus Erythematosus Disease Activity Index 2000; TB=tuberculosis; WOCBP=women of child bearing potential.

- The end of study/safety follow-up visit will occur 4 weeks after the last dose of zetomipzomib or placebo.
- b HBsAg, HBcAb, hepatitis C antibody, and HIV; QuantiFERON®-TB Gold/Gold Plus or T-SPOT® TB test. Positive screens may require additional testing. At Screening, HBcAb-positive patients will have additional tests of HBsAb titer, and hepatitis B DNA to determine eligibility.
- ^c For those HBcAb-positive patients permitted to enter the study (HBcAb positive, HBsAg negative, HBsAb titer ≥100 IU/mL, and negative hepatitis B DNA), additional assessments for hepatitis B DNA should be performed at the indicated visits.
- d A chest x-ray will be obtained during the Screening period if not available from within 90 days prior to signing informed consent form.
- A full physical examination is conducted at Screening visit only. A symptom-directed brief physical examination will be completed at all other visits. Height will be measured at the Screening visit only, and body weight will be collected throughout the study. If visit is being conducted as a telehealth visit, weight will not be collected.
- A 12-lead ECG with QTcF interval should be completed prior to vital signs, following 10 minutes of supine rest at indicated visits. The ECG at Week 25 should also be completed between 30 minutes to 4 hours postdose.
- Vital sign measurements consist of systolic and diastolic blood pressure, pulse rate, and body temperature. Blood pressure and pulse rate should be collected after the patient has had at least 10 minutes of rest in the supine position. When the time of vital sign measurement coincides with a blood sample collection, the vital signs will be measured before blood sample collection or zetomipzomib or placebo administration. A second set of vital signs must be obtained on the Day 1 (Week 1) visit 30 minutes (±15 minutes) after zetomipzomib or placebo has been administered.
- h Clinical lupus disease assessments consist of SLEDAI-2K, SLE Flare Index, 28-Joint Count, and PGA; these assessments should also be performed to document any new or worsening manifestation(s) of SLE.
- i Including the following assessments: HbA1c, total cholesterol, LDL cholesterol and triglycerides (non-fasting)
- Clinical laboratory tests consist of hematology, serum chemistry (non-fasting), urinalysis, and coagulation. When scheduled simultaneously with a dosing visit, samples for clinical laboratory tests should be collected prior to administration of zetomipzomib or placebo. A CBC must be performed locally at approximately Weeks 2, 3, and 4 and as per local practice thereafter in patients who were not already taking MMF or equivalent at Screening and thus started MMF after randomization. After dose increases of MMF or equivalent, CBC must be monitored as per local practice.
- k A urine pregnancy test in WOCBP must be done prior to dose administration.
- 1 IV methylprednisolone on Day 1 ± 7 days; for information on required and permitted background therapies and medications see Sections 6.2.1 and 6.2.2 of the study protocol.

Kezar Life Sciences, Inc. Statistical Analysis Plan, Version 1.0 KZR-616-202

- Once-weekly zetomipzomib or placebo injections are required from Weeks 1 to 52.
- Renal histopathology will be performed during the Screening period if it was not performed 12 months prior the study. Optional renal histopathology and immunohistopathology may be performed at Week 53.
- Blood biomarker measurements consist of cytokine activity, circulating leukocytes, and gene expression/pharmacogenomics and must be done prior to dose administration.

Date Issued: 24Jul2024

- Sparse PK samples will be drawn in all patients at Week 25 at 2 (±15 minutes) hours post dose and at Week 37 at 0.5 (±10 minutes) hours post dose. Optional PK samples will be drawn in a subset of ~30 patients at pre dose and 0.5 (±10) hours, 1 hour (±10 minutes), 2 hours (±15 minutes), and 4 hours (±15 minutes) post dose.
- All AEs must be recorded on the patient's eCRF, starting at the time of informed consent and continuing through 4 weeks post-last dose.

APPENDIX 2. MMF AND ORAL CORTICOSTEROID CONVERSION

MMF

Step 1 – If recorded in mg or ug on eCRF, convert to g.

Step 2 – For MPA or MPS, multiply by conversion factor 1.3888 to get Total Daily Dose (g) in MMF equivalent. Conversion factor is calculated as 1/0.720.

Example: 720 mg MPA x 0.001 g/mg x 1.3888 = 1 g MMF.

Oral Corticosteroids

Corticosteroid	Protocol Table 1
Prednisone	20
Betamethasone	2.4
Cortisone acetate	100
Dexamethasone	3
Hydrocortisone	80
Methylprednisolone	16
Prednisolone	20

Step 1 – If recorded in g on eCRF, convert to mg (multiply by 1000).

Step 2 – Multiply by appropriate conversion factor to get Total Daily Dose (mg) in prednisone equivalent. Conversion factor is calculated as 20/(protocol Table 1 value) to get equivalent of 1 mg prednisone.

Corticosteroid	Conversion factor based on protocol Table 1
Prednisone	1
Betamethasone	8.3333
Cortisone acetate	0.2
Dexamethasone	6.6667
Hydrocortisone	0.25
Methylprednisolone	1.25
Prednisolone	1

Example: 80 mg hydrocortisone x 0.25 = 20 mg prednisone equivalent

APPENDIX 3. AMERICAN COLLEGE OF RHEUMATOLOGY (ACR) / EUROPEAN ALLIANCE OF ASSOCIATIONS FOR RHEUMATOLOGY (EULAR) CRITERIA

Criteria	Definition
Antinuclear antibodies (ANA)	ANA at a titer of ≥1:80 on HEp-2 cells or an equivalent positive test at least once. Testing by immunofluorescence on HEp-2 cells or a solid-phase ANA screening immunoassay with at least equivalent performance is highly recommended
Fever	Temperature >38.3°C
Leukopenia	White blood cell count <4,000/mm³
Thrombocytopenia	Platelet count <100,000/mm³
Autoimmune hemolysis	Evidence of hemolysis, such as reticulocytosis, low haptoglobin, elevated indirect bilirubin, elevated LDH, AND positive Coombs' (direct antiglobulin) test
Delirium	Characterized by 1) change in consciousness or level of arousal with reduced ability to focus, 2) symptom development over hours to <2 days, 3) symptom fluctuation throughout the day, 4) either 4a) acute/subacute change in cognition (e.g., memory deficit or disorientation), or 4b) change in behavior, mood, or affect (e.g., restlessness, reversal of sleep/wake cycle)
Psychosis	Characterized by 1) delusions and/or hallucinations without insight and 2) absence of delirium
Seizure	Primary generalized seizure or partial/focal seizure
Non-scarring alopecia	Non-scarring alopecia observed by a cliniciant
Oral ulcers	Oral ulcers observed by a cliniciant
Subacute cutaneous OR discoid lupus	Subacute cutaneous lupus erythematosus observed by a clinician:† Annular or papulosquamous (psoriasiform) cutaneous eruption, usually photodistributed If skin biopsy is performed, typical changes must be present (interface vacuolar dermatitis consisting of a perivascular lymphohistiocytic infiltrate, often with dermal mucin noted).
	OR Discoid lupus erythematosus observed by a clinician:† Erythematous-violaceous cutaneous lesions with secondary changes of atrophic scarring, dyspigmentation, often follicular hyperkeratosis/plugging (scalp), leading to scarring alopecia on the scalp If skin biopsy is performed, typical changes must be present (interface vacuolar dermatitis consisting of a perivascular and/or periappendageal lymphohistiocytic infiltrate. In the scalp, follicular keratin plugs may be seen. In longstanding lesions, mucin deposition may be noted)
Acute cutaneous lupus	Malar rash or generalized maculopapular rash observed by a cliniciant If skin biopsy is performed, typical changes must be present (interface vacuolar dermatitis consisting of a perivascular lymphohistiocytic infiltrate, often with dermal mucin noted. Perivascular neutrophilic infiltrate may be present early in the course)
Pleural or pericardial effusion	Imaging evidence (such as ultrasound, x-ray, CT scan, MRI) of pleural or pericardial effusion, or both
Acute pericarditis	2 of 1) pericardial chest pain (typically sharp, worse with inspiration, improved by leaning forward), 2) pericardial rub, 3) EKG with new widespread ST elevation or PR depression, 4) new or worsened pericardial effusion on imaging (such as ultrasound, x-ray, CT scan, MRI)
Joint involvement	EITHER 1) synovitis involving 2 or more joints characterized by swelling or effusion OR 2) tenderness in 2 or more joints and at least 30 minutes of morning stiffness
Proteinuria >0.5 g/24 hours	Proteinuria >0.5 g/24 hours by 24-hour urine or equivalent spot urine protein-to- creatinine ratio
Class II or V lupus nephritis on renal biopsy according to ISN/RPS 2003 classification	Class II: Mesangial proliferative lupus nephritis: purely mesangial hypercellularity of any degree or mesangial matrix expansion by light microscopy, with mesangial immune deposit. A few isolated subepithelial or subendothelial deposits may be visible by immunofluorescence or electron microscopy, but not by light microscopy Class V:
	Membranous lupus nephritis: global or segmental subepithelial immune deposits or their morphologic sequelae by light microscopy and by immunofluorescence or electron microscopy, with or without mesangial alterations

Class III or IV lupus nephritis on renal biopsy according to ISN/RPS 2003 classification	Class III: Focal lupus nephritis: active or inactive focal, segmental, or global endocapillary or extracapillary glomerulonephritis involving <50% of all glomeruli, typically with focal subendothelial immune deposits, with or without mesangial alterations Class IV: Diffuse lupus nephritis: active or inactive diffuse, segmental, or global endocapillary or extracapillary glomerulonephritis involving ≥50% of all glomeruli, typically with diffuse subendothelial immune deposits, with or without mesangial alterations. This class includes cases with diffuse wire loop deposits but with little or no glomerular proliferation
Positive antiphospholipid antibodies	Anticardiolipin antibodies (IgA, IgG, or IgM) at medium or high titer (>40 APL, GPL, or MPL, or >the 99th percentile) or positive anti-β,GPl antibodies (IgA, IgG, or IgM) or positive lupus anticoagulant
Low C3 OR low C4	C3 OR C4 below the lower limit of normal
Low C3 AND low C4	Both C3 AND C4 below their lower limits of normal
Anti-dsDNA antibodies OR anti-Sm antibodies	Anti-dsDNA antibodies in an immunoassay with demonstrated ≥90% specificity for SLE against relevant disease controls OR anti-Sm antibodies

^{*} SLE = systemic lupus erythematosus; LDH = lactate dehydrogenase; CT = computed tomography; MRI = magnetic resonance imaging; EKG = electrocardiography; ISN = International Society of Nephrology; RPS = Renal Pathology Society; anti- β_2 -GPI = anti- β_2 -glycoprotein I; anti-dsDNA = anti-double-stranded DNA.

[†] This may include physical examination or review of a photograph.

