## **6.2.1.3.** Mycophenolate Mofetil

Patients will receive background standard of care of "MMF or equivalent," which refers to MMF, MPA, and mycophenolate sodium. MMF 1 g is equivalent to mycophenolate sodium 720 mg.

Oral MMF is a required concomitant medication after randomization, unless the patient is taking equivalent doses of other oral forms, such as MPA and mycophenolate sodium. Patients who are taking other oral forms of mycophenolate may be switched to MMF after randomization at the Investigator's discretion. Patients should be informed of and follow appropriate local practice for this medication, including laboratory monitoring and contraception. MMF will be provided at the sites, or the costs of MMF up to 3 g/day or equivalent will be reimbursed.

Twice daily (BID), 3 times daily (TID) and 4 times daily (QID, if needed due to gastrointestinal AEs) dosing are permitted. The target dose is 2 g/day (e.g., 1 g BID), with doses from 1 g/day to 3 g/day permitted with consultation of the Medical Monitor.

Patients receiving MMF should continue their current dose or, if receiving >2 g/day, will decrease the dose to 2 g/day on Day 1 (Week 1) unless a higher dose (up to 3 g/day) is approved by the Medical Monitor. If >2 g/day is permitted, this dose will not be continued for more than 24 weeks in total nor after Week 25.

For patients who are not currently receiving MMF or equivalent, they will start MMF during the first week (after Week 1 dose of zetomipzomib or placebo) at 1 g/day (0.5 g BID) and increase to 2 g/day (e.g., 1 g BID) during the second week (after Week 2 dose of zetomipzomib or placebo). A complete blood count (CBC) must be performed locally after starting or dose increases. In patients who were not already taking MMF or equivalent at Screening and thus started MMF after randomization, a CBC must additionally be done locally at approximately Weeks 2, 3, and 4 and as per local practice thereafter. After dose increases of MMF or equivalent, CBC must be monitored as per local practice. To aid in distinguishing possible gastrointestinal adverse effects, such as nausea, it is recommended to wait 2 days after the first and second doses of zetomipzomib or placebo, before MMF is started (Day 3) or increased (Day 10), respectively. If a MMF dose of at least 1 g/day is not tolerated, then the patient may be switched to other equivalent forms of mycophenolate at the Investigator's discretion. If a dose of MMF or

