3.2.1.4. Treatment Failure

A patient experiencing one or more of the following criteria define treatment failure:

- Prednisone or equivalent* beyond that permitted (see Section 6.2.1.2 of the study protocol), to include:
 - >10 mg/day for ≥3 consecutive days or for ≥7 days in total during the 8 weeks prior to the renal assessment at
- MMF or equivalent* >2 g/day after Week 25
- Requiring rescue therapy (see Section 6.2.3 of the study protocol for details), as verified by the CEC

Statistical Analysis Plan, Version 1.0 Date Issued: 24Jul2024

• Use of prohibited medications (see Section 6.2.4 and Appendix 2 of the study protocol for details) or inappropriate use of the required concomitant medications (see Section 2.2.5 of the study protocol), as determined through manual data review by the CEC

• Discontinuation of zetomipzomib or placebo

Whenever possible, a complete disease activity assessment (eg, SLEDAI-2K, SLE flare index, PGA) and laboratory assessments (hematology, chemistry, urinalysis, anti-dsDNA, and C3 and C4) should be performed to document flare prior to initiating treatment that results in a treatment failure designation. Treatment failure does not necessarily require discontinuation of zetomipzomib or placebo. See Section 8.1.2 of the study protocol for individual patient stopping rules.

Treatment failure will be adjudicated in blinded fashion by the CEC. Details of this process will be provided in the separate CEC Charter.

*See Appendix 2 for dose conversion of other corticosteroid medications to prednisone equivalent and conversion of mycophenolic acid (MPA) and mycophenolate sodium (MPS) to MMF equivalent.

3.2.1.5. **Relapse**

Relapse is defined as loss of CRR at 2 consecutive time points

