7.1.1.2. Mycophenolate Mofetil (MMF)

All patients will receive daily MMF or equivalent ("MMF") for 52 weeks at a target dose of 2 g/day, in keeping with the standard of care. Doses from 1 g/day to 3 g/day are permitted with consultation of the Medical Monitor.

Patients already receiving MMF at Screening will continue their current dose or, if receiving >2 g/day, will decrease the dose to 2 g/day on Day 1 (Week 1) unless a higher dose (up to 3 g/day) is approved by the Medical Monitor. If >2 g/day is permitted, this dose will not be continued for more than 24 weeks in total nor after Week 25.

Patients who are not receiving MMF at Screening will start MMF during the first week (after Week 1 dose of zetomipzomib or placebo) at 1 g/day and increase to 2 g/day during the second week (after Week 2 dose of zetomipzomib or placebo).

Changes to the patient's MMF dosing regimen are not permitted after Week 25, unless for tolerability issues (Protocol, Section 6.2.1.3). MMF or equivalent dose >2 g/day after Week 25 is considered a treatment failure. Treatment failures will also be independently adjudicated by the CEC, in accordance with procedures documented in the CEC Charter.

All prior MMF use and concomitant use through the end of study will be collected on the "Prior and Concomitant MMF or Equivalent Medications" eCRF form. MMF use will be summarized separately for prior and protocol-required concomitant dosing for both the ITT and Safety Populations.

Prior Use

The number and percentage of patients with any prior MMF use and type of medication used (MMF, MPA, MPS, Other) will be summarized by treatment group. Patients may be included in more than one medication type category.

Concomitant Use (protocol-required dosing)

The following will be summarized by treatment group:

- Number and percentage of patients currently receiving MMF at Screening* (Yes, No)
 - If Yes: Total daily dose at Screening (g/day)
- Average total daily dose (g/day) by study week (Day 1/Week 1 and Week 2 through Week 53)
- Number and percentage of patients with any total daily dose >2 g/day after Week 25 (study day 169)
- Number and percentage of patients with any total daily dose < 1g/day after Week 3 (study day 15)

*Use of MMF at Screening is defined as any use of MMF or equivalent within the 14-day period prior to Screening date.

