As needed, total daily dose as recorded on the eCRF will be converted to MMF equivalent in g/day directly within the EDC system. This derived value will be used for all MMF analyses. Details regarding the derivation are in Appendix 2.

A patient's MMF regimen may be daily, may vary by day(s) of the week (eg, higher dosage Monday-Friday and lower dosage Saturday-Sunday), or have another schedule (eg, every other day) during the course of the study. The eCRF will record the start/stop date and total daily dose associated with each unique regimen for each patient. The total daily dose for each day within the start/stop date interval, inclusive, will be determined based on the regimen. Days within a recorded start/stop date interval with no available dosing information will be assigned a dose of 0.

Total daily dose (g/day) on Day 1 (Week 1) will be summarized separately. For all other study weeks ≥ 2 , average total daily dose (g/day) for Week X will be calculated as {[sum of total daily dose (g/day) over the 7-day period prior to Week X]/7}. The start and stop day (inclusive) of the 7-day period prior to Week X is defined below.

```
Start day of Week X: Day [(X-1)*7-5]
Stop day of Week X: Day [(X-1)*7+1]
```

Average total daily dose (g/day) will only be computed for Week X if there is an available dose value ≥ 0 for every day in the Week X calculation (ie, for all 7 days).

Average total daily dose (g/day) by week will be presented graphically by treatment group for the ITT Population.

• Average total daily dose of MMF from Day 1 through Week 53 (for patients who completed study treatment) and from Day 1 through EOT (for patients who terminated treatment early) will also be summarized by treatment group for the ITT Population.

All MMF or equivalent use will be listed for the ITT Population, with all prior use, protocol-required concomitant use, any concomitant doses <1 g/day or >3 g/day or any doses >2 g/day after Week 25 clearly identified.

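### The rounded factors in SAP Appendix 2 do not match their stated derivations and, applied literally, put some exact-equivalent doses on the wrong side of trial thresholds (low severity)

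*SAP*

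**What the plan says.** Protocol 6.2.1.3 sets the equivalence: "MMF 1 g is equivalent to mycophenolate sodium 720 mg". SAP Appendix 2 implements it: "For MPA or MPS, multiply by conversion factor 1.3888 to get Total Daily Dose (g) in MMF equivalent". It gives the source of the number, "Conversion factor is calculated as 1/0.720", and a worked case: "Example: 720 mg MPA x 0.001 g/mg x 1.3888 = 1 g MMF". For steroids it states "Conversion factor is calculated as 20/(protocol Table 1 value) to get equivalent of 1 mg prednisone" and then tabulates four-decimal factors, including 6.6667 for dexamethasone and 8.3333 for betamethasone.

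These conversions feed the analysis. SAP 7.1.1.2 places the MMF conversion in the EDC and adds: "This derived value will be used for all MMF analyses". SAP 7.1.1.3 does the same for analyses of protocol-required oral corticosteroids. The treatment-failure definition in SAP 3.2.1.4 points to the same place: "See Appendix 2 for dose conversion of other corticosteroid medications to prednisone equivalent".

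The thresholds are sharp:
- MMF below 1 g/day after Week 3: a summary count and a listing flag (SAP 7.1.1.2).
- MMF above 2 g/day after Week 25: treatment failure (SAP 3.2.1.4 and 7.1.1.2).
- Prednisone equivalent above 10 mg/day, on at least 3 days running or at least 7 days altogether in the 8 weeks before the renal assessment: treatment failure (Protocol 2.2.5; SAP 3.2.1.4 and 7.1.1.3).
- Prednisone equivalent of at most 5 mg/day at Week 17: a summary (SAP 7.1.1.3), and part of the taper-conditioned secondary and exploratory endpoints (SAP 8.4.3 and 8.5.3).

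**The concern.** The cut-offs of 1 g, 2 g, 5 mg and 10 mg are round numbers that some products hit exactly after conversion. At such a point any rounding error in the factor, however small, decides the classification. SAP Section 4 sets decimals for display only, and no section says that a converted dose is rounded before it is tested. A programmer who follows the printed factors would therefore get wrong flags for these doses. What is at stake is the count of patients below 1 g/day, the steroid summaries, the taper-conditioned endpoints and the programmed treatment-failure flag.

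**Working it through.** **Inputs.** From SAP Appendix 2: factors 1.3888 (MPA/MPS), 6.6667 (dexamethasone) and 8.3333 (betamethasone). From Protocol Table 1, doses equal to 20 mg prednisone: dexamethasone 3 mg, betamethasone 2.4 mg. From Protocol 6.2.1.3: 720 mg mycophenolate sodium = 1 g MMF.

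**The SAP's own example first.** 720 × 0.001 × 1.3888 = 0.999936 g, not 1 g. The stated result appears only if the product is rounded to three decimals or fewer. The derivation gives 1/0.720 = 1.388889, so the printed factor is low by 0.0064% (1 − 0.999936).

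**Dexamethasone.** 20/3 = 6.666667, so 6.6667 is high by 0.0005% (0.00005/10).

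**Each dose against its threshold**

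| Daily dose | Exact ratio | Printed factor | Threshold | Result |
|---|---|---|---|---|
| MPA/MPS 720 mg | 720/720 = 1 g | 0.720 × 1.3888 = 0.999936 g | <1 g | wrongly met |
| MPA/MPS 1440 mg | 1440/720 = 2 g | 1.440 × 1.3888 = 1.999872 g | >2 g | correctly not met |
| MPA/MPS 2160 mg | 2160/720 = 3 g | 2.160 × 1.3888 = 2.999808 g | >3 g | correctly not met |
| Dexamethasone 1.5 mg | 1.5 × 20/3 = 10 mg | 1.5 × 6.6667 = 10.00005 mg | >10 mg | wrongly met |
| Dexamethasone 0.75 mg | 0.75 × 20/3 = 5 mg | 0.75 × 6.6667 = 5.000025 mg | ≤5 mg | wrongly missed |
| Betamethasone 1.2 mg | 1.2 × 20/2.4 = 10 mg | 1.2 × 8.3333 = 9.99996 mg | >10 mg | correctly not met |

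The other five steroid factors (1, 1, 0.2, 0.25 and 1.25) are exact.

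**The tempting repair.** With 1.3889, 720 mg gives 1.000008 g, which is no longer below 1 g. But 1440 mg gives 1.440 × 1.3889 = 2.000016 g, which is above 2 g. That would move the error from a descriptive count to a treatment-failure criterion, for patients at the equivalent of the 2 g/day target.

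**Effect of rounding.** To three decimals, 0.999936 becomes 1.000, 10.00005 becomes 10.000 and 5.000025 becomes 5.000. All three misclassifications disappear.

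**The case against.** The best defence is that the intention is plain. Appendix 2 prints the exact derivations beside the factors, and its example equates 720 mg with 1 g. The conversion runs in the EDC, whose code is not shown; it may already use the exact ratio or round the result. This stands as a limit on the consequence: one cannot say that every patient at these doses will be misclassified, only that they would be if the printed factors are coded as written. It does not excuse a specification whose worked example is numerically false.

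A reader might infer that the truncated MMF factor creates false treatment failures. It does not. The below-1 g rule is not a failure criterion in Protocol 2.2.5 or SAP 3.2.1.4, and at the 2 g limit the printed factor classifies 1440 mg correctly.

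A reader might also infer that the dexamethasone factor distorts the primary endpoint. The documents do not support that. SAP Table 4 defines the intercurrent event as failure adjudicated by the CEC, SAP 3.2.1.4 makes that adjudication blinded, and SAP 8.2 uses the adjudicated endpoint for the primary analysis. Protocol 6.2.1 also lets the Medical Monitor accept deviations of around 20%, far above 0.0005%. A patient would have to be held at exactly 1.5 mg/day for long enough inside the 8-week window. What remains exposed is the non-adjudicated programmed endpoint, which SAP 8.2 retains, and the steroid summaries, for which no adjudication is mentioned.

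Nor do all the rounded factors fail: betamethasone at 1.2 mg stays on the right side.

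**Conclusion.** The appendix is wrong as written, at low severity. The printed factors for MPA/MPS and dexamethasone disagree with their stated derivations, and no rounding rule protects the comparisons. Under literal coding, 720 mg MPA/MPS is counted as below 1 g/day in one summary and one listing. Dexamethasone 1.5 mg meets the programmed 10 mg criterion, and 0.75 mg misses the 5 mg target in the Week 17 summary and the taper-conditioned endpoints, which lie outside the multiplicity control. Any effect on CRR at Week 37 is likely negligible.

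This rests on two assumptions: that the EDC or analysis code uses the printed factors, and that it does not round the product. The documents settle neither, and they do not give the number of patients taking MPA, mycophenolate sodium or dexamethasone, so the number affected cannot be estimated.

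**What to change.** In Appendix 2, replace the decimal factors with the exact ratios: MMF equivalent in g = dose in mg / 720, and prednisone equivalent in mg = dose in mg × 20 / Protocol Table 1 value. Add one sentence saying that the converted daily dose is rounded, for example to two decimals, before any comparison with a threshold. Apply the same rule in the EDC or analysis derivation, check which factor is coded now, and regenerate the derived doses if it is the printed one. Do not substitute 1.3889 for 1.3888. The change restores the equivalences the protocol already states and alters no dose or clinical rule. It costs a short SAP edit and a small derivation change.
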